11.5.6 Exploratory Analyses**Intradermal Allergen Challenge****Wheal/Flare Derivations**

- The wheal and flare derived value to be used in the summaries and figures will be calculated as follows:
- At each planned timepoint both the Wheal (also referred to as Induration in some study documents) and Flare components will have two measurements databased; namely the longest and orthogonal diameters. The mean diameter for each component is the average of these two values. For display purposes the label “Wheal” should be used rather than “Induration”. An example is illustrated below

Intradermal Allergen Challenge

- Mean Diameter (Wheal) = $(A1+A2) / 2$
- Mean Diameter (Flare) = $(B1+B2) / 2$
- For each subject and planned sampling time the Mean Diameter Wheal values for each allergen should be compared to the corresponding Negative control value as an additional data validation check. A flag variable should capture if the Mean Diameter Wheal response on Challenge not at least 3mm larger than the corresponding Negative control value (i.e. flag if Wheal Mean Diameter Challenge – Wheal Mean Diameter Negative Control Challenge $\leq 3\text{mm}$).

Total Nasal Symptom Score (Diary card)

Daily Score Derivation (TNSS and its individual components) – daily scores sometimes referred to as “Overall”

- The Daily Score is calculated as the mean of the (non-missing) respective AM and PM assessments (e.g. Daily TNSS = Mean of AM TNSS and PM TNSS values; Daily nasal congestion score = Mean of AM nasal congestion score and PM nasal congestion score, etc. A daily score would only be recorded as missing if both the AM and PM assessment are missing on that day.

Weekly Weighted Mean Derivation

- Each diary card week begins on the planned day of dosing (relative to the date of dosing at DV1) and contains 7 days of data, i.e. Week 1 contains days 1 to 7 inclusive, Week 2 contains days 8 to 14 inclusive etc.
- The weekly weighted means are derived from the 7 days of data using a similar approach to the BAC endpoints. The exceptions are i) no actual time, but only planned times, starting at 1 and ending at 7 for each weeks worth of data, ii) the first and last values (day 1 and 7 within the week) may be missing and a valid WM derived (the

Total Nasal Symptom Score (Diary card)

WM would only not be derived if 4 or more days within the week were missing; in which case the Weekly WM would also be set to missing) and iii) No BAC specific rules e.g. setting WM means to missing based on rescue medication, SABA or incorrect BAC allergen administration.

- If the number of missing WM values is considered to be substantial, or if the data is not considered to be missing at random, a sensitivity analysis may be carried out with respect to methods of handling missing data in the calculation of the weighted mean.

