### 4.2. Treatment Arms and Duration

- The study will consist of a screening period of up to approximately 4 weeks (involving two screening visits), a blinded treatment period of 8 weeks, followed by a follow-up period of up to 3 months. The total duration of the study for each subject will therefore be a maximum of approximately 6 months. All doses will be administered in the clinic.
- Approximately 24 subjects per treatment arm will be randomised in a 1:1 ratio to receive either i.n. 20ng GSK2245035 or placebo every week for the duration of 8 weeks.

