### 7.3.2. Intranasal and intra-dermal allergen challenge

NAC and ID challenge will be conducted approximately 24 hours after the bronchial allergen challenge at screening and at follow-up visits 1 and 2.

A detailed description of the NAC and ID challenges can be found in the SRM.

*In some regions/countries specific challenges agents may not be approved or available for use in ID challenge, in which case this assessment shall be omitted.*

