#### **7.3.4. TNSS**

Four nasal symptoms: nasal congestion, rhinorrhea, nasal itch and sneezing will be evaluated on the morning and evening of each day of the study treatment period, from DV1 up until follow-up visit 2 (4 weeks after the end of treatment). These will be captured on a diary card every morning and evening. On dosing days, the morning TNSS assessment will be captured pre-dose. The subjects will be asked to rate each of these symptoms on a 4-point scale:

0 = None: No symptom whatsoever; Absent

1 = Mild: Symptom is present, noticeable but not bothersome

2 = Moderate: Symptom is bothersome, but tolerable

3 = Severe: Symptom which are bothersome, harder to tolerate, desiring relief/treatment

The individual symptom scores will be combined to produce a TNSS.

All data will be transcribed from the diary booklet into the CRF.

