9 EXPLORATORY STATISTICAL ANALYSES

9.1 Exploratory Analyses

9.1.1 Overview of Planned Exploratory Analyses

The exploratory analyses will be based on different populations depending on what the endpoint is.

Table 16 provides an overview of the planned exploratory analyses, with further details of data displays being presented in [Appendix 13: List of Data Displays](#).

Table 16 Overview of Planned Exploratory Analyses

Endpoint	Absolute							
	Stats Analysis			Summary		Individual		
	T	F	L	T	F	F	L	
TNSS								
WM TNSS by Week	Y		Y		Y		Y	
WM Individual Components of TNSS by Week	C		C		C		C	

NOTES :

- T = Table, F = Figure, L = Listing, Y = Yes display generated, C=Display conditional on other results.
- Stats Analysis = Represents TFL related to any formal statistical analyses (i.e. modelling) conducted.
- Summary = Represents TFL related to any summaries (i.e. descriptive statistics) of the observed raw data.
- Individual = Represents FL related to any displays of individual subject observed raw data.

Intradermal Allergen Challenge	Log Untransformed											
	Absolute						Change from Baseline					
	Stats Analysis			Summary		Individual	Stats Analysis			Summary		Individual
	T	F	L	T	F	F	L	T	F	L	T	F
Mean Diameter Early Phase Response (15m)												
Wheal/Flare data	C	C	C	Y			Y			Y	Y	Y
Mean Diameter Late Phase Response (6h)												
Wheal/Flare data	C	C	C	Y			Y			Y	Y	Y

NOTES :

- T = Table, F = Figure, L = Listing, Y = Yes display generated, C=Display conditional on other results.
- Stats Analysis = Represents TFL related to any formal statistical analyses (i.e. modelling) conducted.
- Summary = Represents TFL related to any summaries (descriptive statistics) of the observed raw data.
- Individual = Represents FL related to any displays of individual subject observed raw data.

Weighted Mean TNSS

The weighted means of the TNSS values (AM and PM values combined into an overall daily score prior to deriving WM) will be derived for each diary card week. They will be analysed using a similar model to FeNO (Section [8.4.2.3.5](#)) except the response is not anticipated to require any transformation, so the model should be modified to examine differences and not ratios and to account for the additional Follow Up Visit timepoints.

Baseline would be the Day 1 AM TNSS value and Visit would be the week (of each weighted mean).

Conditional on the above output the following may be attempted (and would be assigned the next available output number):

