11.13.14 Exploratory Figures

Exploratory: Figures					
No.	Population	IDSL / TST ID / Example Shell	Title	Programming Notes	Deliverable [Priority]
Intradermal Allergen Challenge					
6.1.	All Subjects	EFF_F2	Intradermal Allergen Challenge: Boxplots of derived Change from Baseline in Mean Diameter Early/Late Phase Wheal/Flare By Visit and Treatment/Allergen Strata Combinations	
Overlay individual data points next to boxes (but do not obscure key features such as mean/median symbols and whiskers/outliers)
 
Use default SAS boxplot type
 
Deviate from treatment/strata colour schemes if necessary to display all information types (e.g. use different box fill colours/patterns for presumed and unknown allergen strata)
 
Response variable is the derived change from baseline (SV)
 
Separate page for Wheal and Flare responses
 
Row categories are Early phase (15m timepoint) and Late phase (6h timepoint)
 
Columns are Visits (FUV1 and FUV2)
 
Add horizontal ref line(s) at zero
	FSP: SAC 2

Exploratory: Figures					
No.	Population	IDSL / TST ID / Example Shell	Title	Programming Notes	Deliverable [Priority]
Weighted Mean Total Nasal Symptom Score (TNSS)					
6.2.	All Subjects	PD_F3	WM TNSS: Summary profiles of Weekly WM TNSS data by Week	Separate Figure/Page for Overall TNSS and the AM and PM versions. Do not include the mean and 95% CI profiles for the allergen exposure strata (grey lines in shell) If necessary to improve clarity/readability of figure display CIs for a subset of the timepoints (e.g. Week 1, 4, 8, FUV1, FUV2)	FSP: SAC [2]
6.3.	All Subjects	PD_F6	WM TNSS: Point estimates and 95% Credible Intervals from the Analysis of Weekly WM TNSS data		FSP: SAC 2
6.4.	All Subjects	EFF_F6	WM TNSS: Posterior Distribution Density Plots from the Analysis of Weekly WM TNSS data		FSP: SAC 2
6.5.	All Subjects	PD_F3	WM TNSS: Summary profiles of Weekly WM TNSS component data by Week	Conditional. As per TNSS equivalent	FSP: SAC [2]
6.6.	All Subjects	PD_F6	WM TNSS: Point estimates and 95% Credible Intervals from the Analysis of Weekly WM TNSS component data	Conditional. As per TNSS equivalent	FSP: SAC 2
6.7.	All Subjects	EFF_F6	WM TNSS: Posterior Distribution Density Plots from the Analysis of Weekly WM TNSS component data	Conditional. As per TNSS equivalent	FSP: SAC 2

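### On schedule, the SAP's diary-week rule makes the Week 9 TNSS mostly days on or after the nasal challenge, leaves Week 12 derivable only for late attenders, and counts the baseline score inside Week 1

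*SAP*

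**What the plan says.** SAP 11.5.6, under Total Nasal Symptom Score (Diary card), sets the weeks: "Each diary card week begins on the planned day of dosing (relative to the date of dosing at DV1) and contains 7 days of data". Its own illustration is that "Week 1 contains days 1 to 7 inclusive, Week 2 contains days 8 to 14 inclusive". The weekly weighted mean (WM) uses the trapezoidal rule on planned days 1 to 7. On missing days, the "WM would only not be derived if 4 or more days within the week were missing". None of the SAP's challenge-related exclusions applies to the diary score.

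SAP 9.1.1 extends the TNSS model to follow-up time points and sets the covariate: "Baseline would be the Day 1 AM TNSS value". The daily score averages the available morning and evening scores (SAP 11.5.6), and on dosing days the morning score is taken before the dose (Protocol 7.3.4). The programming note for Figure 6.2 (SAP 11.13.14) gives examples of time points to show: "e.g. Week 1, 4, 8, FUV1, FUV2". The SAP does not state which diary week is FUV1 or FUV2.

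Protocol 7.3.2 says "NAC and ID challenge will be conducted approximately 24 hours after the bronchial allergen challenge at screening and at follow-up visits 1 and 2". Protocol 7.3.4 has TNSS recorded "from DV1 up until follow-up visit 2 (4 weeks after the end of treatment"). The follow-up Time and Events table (Protocol 7.1.3) has the card returned at the 24-hour visit after FUV2.

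**The concern.** The diary weeks follow the first-dose date, while the challenges and the end of recording follow the visits. On schedule, three things result.

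- Week 9, the first diary week starting after the last dosing week, opens on the day of the FUV1 bronchial challenge and has the NAC on its second day. Protocol 4.4 reports that the earlier 8-week study saw lower TNSS 15 minutes after an NAC. A Week 9 difference could therefore reflect a smaller response to the challenge and be read as lasting benefit on natural symptoms.
- Recording stops at the start of Week 12, so the week matching FUV2 is nearly empty.
- A score taken before any drug is both the covariate and part of the Week 1 response.

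At stake is the reading of the exploratory follow-up TNSS results. The optional multivariate analyses (SAP 8.4.3.3) may also use weekly TNSS by subject and visit, so they need the same mapping.

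**Working it through.** **Calendar.** Week w covers Days 7(w-1)+1 to 7w. This reproduces the SAP's Days 1-7 and 8-14. Dosing is weekly (Protocol 4.2: "placebo every week for the duration of 8 weeks"). With DV1 on Day 1:

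- DV8 = 1 + 7×7 = Day 50
- FUV1 = 50 + 7 = Day 57; NAC = Day 58
- FUV2 = 50 + 28 = Day 78; card returned Day 79
- Week 8 = Days 50-56; Week 9 = Days 57-63; Week 11 = Days 71-77; Week 12 = Days 78-84

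**Which weeks are FUV1 and FUV2.** Protocol 7.1.3 labels the two visits Week 9 and Week 12. The Figure 6.2 note lists Week 8 and FUV1 as separate points. Weeks 9 and 12 are therefore the best-supported reading, though the SAP does not state it.

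**Weights.** The trapezoid on seven equally spaced days gives 0.5/6 = 8.3% to each end day and 1/6 = 16.7% to each of the five interior days.

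**Week 9, on schedule.** Only Day 57 precedes the NAC day, so the share on or after it is 1 - 0.5/6 = 11/12 = 91.7%. The NAC follows the 24-hour sputum and blood samples, so the Day 58 morning score may come first. The share is then 91.7% - ½×16.7% = 83.3%.

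**Week 12, on schedule.** Days 78 and 79 are the most that can be recorded. Five days are missing, which exceeds the limit, so no value is derived.

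**Visit timing.** Protocol section 7 leaves visit windows to the Study Reference Manual, so lateness against the first-dose calendar is an assumption, ranged here:

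| Days late | Week 9 days on/after NAC | Weight | Weight if NAC-day AM score is pre-NAC | Week 12 days recorded (to 24 h after FUV2) | Week 12 derived? | Derived if recording stops on FUV2 day? |
|---|---|---|---|---|---|---|
| 0 | 6 | 91.7% | 83.3% | 2 | No | No |
| 1 | 5 | 75.0% | 66.7% | 3 | No | No |
| 2 | 4 | 58.3% | 50.0% | 4 | Yes | No |
| 3 | 3 | 41.7% | 33.3% | 5 | Yes | Yes |

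Week 9 columns use FUV1 lateness; Week 12 columns use FUV2 lateness. Week 11 is complete when FUV2 is on schedule or late.

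**Baseline in Week 1.** Day 1 carries 0.5/6 of the week, and the morning score is half of the Day 1 value: ½ × 0.5/6 = 4.2% of the overall WM. In the AM-only WM, or if the Day 1 evening score is missing, it is 0.5/6 = 8.3%.

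**The case against.** The strongest reply is that the arithmetic concerns dates and not symptoms. Neither document says how long nasal symptoms last after an NAC, and the TNSS reduction in the previous 8-week study was at 15 minutes. Both arms have the same planned challenge. All of this stands. A reader might infer that Week 9 is contaminated for days, or that its treatment comparison is invalid; the documents support neither. What remains is that the Week 9 contrast mixes natural and provoked symptoms in an unknown proportion.

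A reader might also infer that the FUV2 value is missing for every subject. That goes too far: a late enough FUV2 yields a value, and if FUV2 was meant to be Week 11 the value is derivable on schedule. Under the better-supported Week 12 reading, however, availability depends on attending late, which is a poor basis for an estimate.

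The baseline overlap is small. The model borrowed from the FeNO analysis has a separate baseline slope for each week (SAP 8.4.2.3.5), and that slope absorbs a fixed multiple of baseline. The overlap therefore dilutes the overall Week 1 effect by about 4% and does not bias the adjusted comparison.

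Finally, the protocol endpoint is TNSS through the treatment phase, and on schedule Weeks 1-8 precede every follow-up challenge. SAP 11.5.6 also allows a sensitivity analysis if many weekly means are missing. Both points limit the consequence, but neither corrects the day mapping.

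**Conclusion.** The point holds as a low-cost improvement to an exploratory analysis. With visits on schedule, 91.7% of the Week 9 weight (83.3% under the morning-score assumption) lies on or after the NAC, and the share is still 75% or 58% if FUV1 is 1 or 2 days late. Week 12 is set to missing for every subject whose FUV2 is on schedule or up to 1 day late. It is derivable only from 2 days late, or from 3 if recording stops on the FUV2 day. The Week 1 overlap is 4.2% (8.3% for AM-only).

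These results rest on weekly dosing as planned, on Weeks 9 and 12 standing for FUV1 and FUV2, and on visit windows that the documents do not give. The primary and secondary analyses are unaffected.

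**What to change.** Amend SAP 11.5.6 and 9.1.1 before unblinding:

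- Define the FUV2 TNSS as the 7 days ending the day before the subject's actual FUV2 bronchial challenge (Days 71-77 on schedule, where it coincides with Week 11 and should replace it). Do not model a Week 12 value.
- Keep Week 8 (Days 50-56) as the last week before the FUV1 challenges.
- Label Week 9 as containing the bronchial and nasal challenges, and report its post-NAC days (Days 58-63 on schedule) separately. Do not read it as persistence of effect on natural symptoms; Weeks 10-11 serve that purpose. Whether Week 9 stays in the repeated-measures model is a matter of judgement, and the documents do not require its removal.
- Start the Week 1 response with the Day 1 evening score. The AM-only version then starts on Day 2, which the SAP's rule already permits because the first day of a week may be missing.

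The cost is SAP wording and a small re-mapping of days already collected, with slightly less data in Weeks 1 and 9.

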11.6 Appendix 6: Premature Withdrawals & Handling of Missing Data

11.6.1 Premature Withdrawals

Element	Reporting Detail
General	
 Subject study completion (i.e. as specified in the protocol) was defined as one who has completed all phases of the study including all of the follow-up visits. Withdrawn subjects may be replaced in the study. All available data from subjects who were withdrawn from the study will be listed and all available planned data will be included in summary tables and figures, unless otherwise specified.

11.6.2 Handling of Missing Data

Element	Reporting Detail
General	
 Missing data occurs when any requested data is not provided, leading to blank fields on the collection instrument : 
 These data will be indicated by the use of a “blank” in subject listing displays. Unless all data for a specific visit are missing in which case the data is excluded from the table. Answers such as “Not applicable” and “Not evaluable” are not considered to be missing data and should be displayed as such.
Outliers	
 Any subjects excluded from the summaries and/or statistical analyses will be documented along with the reason for exclusion in the clinical study report.

11.6.2.1 Handling of Missing Dates

Element	Reporting Detail
General	Partial dates will be displayed as captured in subject listing displays.
Adverse Events	
 The eCRF allows for the possibility of partial dates (i.e., only month and year) to be recorded for AE start and end dates; that is, the day of the month may be missing. In such a case, the following conventions will be applied for calculating the time to onset and the duration of the event: 
 Missing Start Day: First of the month will be used unless this is before the start date of study treatment; in this case the study treatment start date will be used and hence the event is considered On-treatment as per Appendix 3: Treatment States and Phases. Missing Stop Day: Last day of the month will be used, unless this is after the stop date of study treatment; in this case the study treatment stop date will be used. Completely missing start or end dates will remain missing, with no imputation applied. Consequently, time to onset and duration of such events will be missing.

Element	Reporting Detail
	
 Start or end dates which are completely missing (i.e. no year specified) will remain missing, with no imputation applied.

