#### **4.4. Design Justification**

- GSK2245035 is currently being developed for patients with allergic asthma. It has been studied in healthy volunteers (HVT) and subjects with allergic rhinitis with and without mild asthma.
- This study will assess the safety, target engagement, and efficacy of GSK2245035 in subjects with allergic asthma using a placebo-controlled, parallel group design and a BAC model. The BAC model is an established methodology and will be used in this study to determine whether 8 weekly doses of 20 ng i.n. GSK2245035 attenuates allergen-induced asthmatic responses compared to placebo. In addition to the assessment after BAC at the end of the 8-week treatment (1 week after the 8th dose), additional BACs will be performed at approximately 4 weeks and 12 weeks after the 8th dose to assess the durability of the effect.
- In an 8-week repeat dose safety study TL7116958 [GlaxoSmithKline Document Number [2013N174200\\_00](#)], there was a reduction of TNSS at 15 minutes post-NAC. This could indicate an effect of GSK2245035 treatment on mast cell activation and mediator release. In the current study, nasal lining fluid will be collected before and up to 5 minutes after nasal allergen challenges to evaluate the impact of GSK2245035 on mast cell mediator release. NACs will be performed approximately 24 hours after the BACs that are conducted at screening and at approximately 1 week and 4 weeks after the final dose.
- Interim analysis: Previous experience within GSK suggests some individuals (approximately 20%) fail to demonstrate a LAR response after the screening visit (i.e. they pass the screening criteria but do not demonstrate another LAR response when receiving placebo during the on-treatment phase). Those GSK studies were mainly crossover designs with a placebo in every sequence, so subjects who did not demonstrate a post screening LAR could be retrospectively identified and excluded from the statistical analyses. However this study has parallel groups and the profiles of a “perfect” drug effect and an inconsistent LAR subject are indistinguishable so retrospective exclusions cannot be made for the GSK2245035 arm. If the rate of “non-reproducible LAR” subjects is large it will reduce the probability of success.

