#### 7.4.1.1. Time period and Frequency for collecting AE and SAE information

Any SAEs assessed as related to study participation (e.g., protocol-mandated procedures, invasive tests, or change in existing therapy) or related to a GSK product will be recorded from the time a subject consents to participate in the study up to and including the final follow-up visit.

AEs will be collected from the start of Study Treatment until the final follow-up visit (see Section 7.4.1.3), at the time-points specified in the Time and Events Table (Section 7.1).

Medical occurrences that begin prior to the start of study treatment but after obtaining informed consent may be recorded on the Medical History/Current Medical Conditions section of the CRF.

All SAEs will be recorded and reported to GSK within 24 hours, as indicated in [Appendix 4](#).

Investigators are not obligated to actively seek AEs or SAEs in former study subjects. However, if the investigator learns of any SAE, including a death, at any time after a subject has been discharged from the study, and he/she considers the event reasonably related to the study treatment or study participation, the investigator must promptly notify GSK.

NOTE: The method of recording, evaluating and assessing causality of AEs and SAEs plus procedures for completing and transmitting SAE reports to GSK are provided in [Appendix 4](#).

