11.3.2.1 Treatment States for AE (and DRE) Data

Treatment State	Definition
Pre-Treatment	AE Start Date/Time < Study Treatment Start Date/Time
On-Treatment*	If AE onset date/time is on or after treatment start date/time & on or before treatment stop date/time. Study Treatment Start Date/Time ≤ AE Start Date/Time ≤ Study Treatment Stop Date/Time + 7
Post-Treatment*	If AE onset date is after the treatment stop date. AE Start Date > Study Treatment Stop Date + 7
Onset Time Since 1 st Dose (Days)	If Treatment Start Date > AE Onset Date = AE Onset Date – Treatment Start Date If Treatment Start Date ≤ AE Onset Date = AE Onset Date – Treatment Start Date + 1 Missing otherwise.
Duration (Days)	AE Resolution Date – AE Onset Date + 1
Drug-related ^Δ	If relationship is marked 'YES' on eCRF OR value is missing

NOTES:

- * Treatment phase assumes that the effects of study treatment duration will last a week.
- Study Treatment Start relates to the 1st dose received by the individual and the Study Treatment Stop relates to the final dose received by the individual. If the study treatment stop date is missing then the AE will be considered to be On-Treatment.
- Δ=Not applicable/required for DRE

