11.6.2.2 Handling of Partial Dates

Element	Reporting Detail
Concomitant Medications	
 Partial dates for any concomitant medications recorded in the CRF will be imputed using the following convention: 
 If the partial date is a start date, a '01' will be used for the day and 'Jan' will be used for the month If the partial date is a stop date, a '28/29/30/31' will be used for the day (dependent on the month and year) and 'Dec' will be used for the month. The recorded partial date will be displayed in listings.
Adverse Events	
 Any partial dates for adverse events will be raised to data management. If the full date cannot be ascertained, the following assumptions will be made: 
 If the partial date is a start date, a '01' will be used for the day and 'Jan' will be used for the month. However, if this results in a date prior to Week 1 Day 1 and the event could possibly have occurred during treatment from the partial information, then the Week 1 Day 1 date will be assumed to be the start date. The AE will then be considered to start on-treatment (worst case). If the partial date is a stop date, a '28/29/30/31' will be used for the day (dependent on the month and year) and 'Dec' will be used for the month. The recorded partial date will be displayed in listings.

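### SAP 11.6.2.1 caps an imputed AE stop date at the last dose, which gives zero or negative durations for AEs that start later, and SAP 11.6.2.2 contradicts it

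*SAP*

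**What the plan says.** SAP 11.6.2.1 covers AE dates with a known month and year but no day, and states its purpose: "the following conventions will be applied for calculating the time to onset and the duration of the event". A missing stop day becomes the last day of the month, "unless this is after the stop date of study treatment; in this case the study treatment stop date will be used". The rule makes no exception for AEs that begin after treatment has ended and sets no floor at the onset date. The companion start-day rule does have a floor, at the start of treatment.

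SAP 11.3.2.1 supplies the two definitions that matter. Duration is "AE Resolution Date – AE Onset Date + 1", and "the Study Treatment Stop relates to the final dose received by the individual".

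Protocol 7.4.1.1 sets the collection window: "AEs will be collected from the start of Study Treatment until the final follow-up visit". Protocol 4.4 describes what happens late in that window: "additional BACs will be performed at approximately 4 weeks and 12 weeks after the 8th dose". The one-week challenge also falls after the last dose.

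SAP 11.6.2.2 then gives a second rule for partial AE dates. They are first queried with data management. If the full date cannot be found, 28, 29, 30 or 31 "will be used for the day (dependent on the month and year") of a stop date, and December for the month. The treatment stop date is not mentioned. The SAP does not say which of the two sections takes precedence.

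**The concern.** A cap at treatment stop would be harmless if AE collection ended with treatment. Here it does not: roughly 12 weeks of collection, including three bronchial challenges, come after the last dose. For an AE that starts in that period, the cap date is already in the past when the event begins. An imputed stop set there cannot be right.

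The second problem is the pair of rules. Two programmers working from adjacent sections of one SAP could derive different durations for the same event, and both would be following the plan.

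What is at stake is a derived safety variable. Duration has been used for this compound before: the risk assessment in Protocol 4.6.1 cites a median duration of about a day or less for cytokine-related AEs. An event of that kind with onset on the day of the last dose and a missing stop day would be given exactly one day by the cap. One starting the next day would be given zero.

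**Working it through.** The documents state no figure to reproduce, so the check applies the rules as written.

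**Inputs**
- Treatment stop T = date of the final dose (SAP 11.3.2.1).
- Stop-day rule A: the earlier of month end and T (SAP 11.6.2.1).
- Stop-day rule B: month end, no cap (SAP 11.6.2.2). I read December as applying only when the month is also missing, because the day is said to depend on the month.
- Duration = resolution − onset + 1 (SAP 11.3.2.1).
- AE collection to the final follow-up visit, about 84 days after the 8th dose plus a 24-hour return (Protocol 7.4.1.1, 4.4 and 7.1.3).

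**General result.** Let onset = T + k with k ≥ 1, and let the recorded stop month be no earlier than the onset month. Month end is then on or after the onset, hence after T, and rule A always sets the stop to T:

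duration = T − (T + k) + 1 = 1 − k.

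The imputed stop is always before the onset. Duration is 0 for k = 1 and negative for every k ≥ 2.

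**Worked example.** Last dose 28 March, onset 10 April, stop recorded only as April. From 28 March to 10 April is 3 + 10 = 13 days, so k = 13.
- Rule A: stop 28 March, duration 1 − 13 = −12 days.
- Rule B: stop 30 April, duration 30 − 10 + 1 = +21 days.

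**Illustrative schedule** (assumed dates: first dose 1 March 2017, eighth dose 49 days later on 19 April, final visit on 12 July with its 24-hour return on 13 July). The onset date is known, and the stop is recorded only as the month of onset.

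| Onset relative to last dose (days) | Onset | Rule A (days) | Rule B (days) |
|---|---|---|---|
| −5 | 14 April | 6 | 17 |
| 0 | 19 April | 1 | 12 |
| +1 | 20 April | 0 | 11 |
| +2 | 21 April | −1 | 10 |
| +7 | 26 April | −6 | 5 |
| +28 | 17 May | −27 | 15 |
| +84 | 12 July | −83 | 20 |

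The first two rows show the other effect: an AE that starts on or before the last dose keeps a positive duration but can be shortened. The +7 row shows that the fault is not confined to the post-treatment state, since SAP 11.3.2.1 still counts onsets up to 7 days after the last dose as on-treatment.

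**All calendar alignments.** Taking every first-dose date in a year and onsets from +1 to +85 days, rule A gives durations from 0 to −84. Negative values arise for 84 of the 85 onset days (98.8%). This is a share of possible onset days, not of AEs.

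**Rule B is not perfect either.** In the +84 row it places the stop at 31 July, 18 days after the subject was last seen on 13 July. Stopping at last contact would give 13 − 12 + 1 = 2 days.

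**The case against.** The strongest reply is that very little hangs on this, and most of that reply stands.

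- Only AEs with a missing stop day are affected, and SAP 11.6.2.2 sends partial dates to data management before anything is imputed. The documents give no rate of partial dates, so the number of affected AEs is unknown and may be small.
- No planned AE summary is shown to use duration. The overview in SAP 8.2.1 and safety tables 3.1 to 3.9 in SAP 11.13.7 report system organ class, relatedness, severity, seriousness and CRS frequency. The mock shells are a separate document, so whether a listing prints duration cannot be checked here.
- On- or post-treatment status depends on onset, so classification and incidence do not move. Recorded partial dates remain visible in listings.
- If 11.6.2.2 were taken to govern, no negative duration would arise when the start date is known.

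The last argument does not clear the plan. Nothing in the SAP gives 11.6.2.2 precedence, and 11.6.2.1 is the section that says it is for computing duration.

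A reader might infer more than the documents support. One inference is that follow-up AE durations in general would be impossible or too short; that drops the missing-day condition. Another is that the roughly 12 weeks after the last dose measure the share of AEs affected; they measure calendar time only. A third is that safety after treatment is a stated aim. The safety objective in Protocol section 3 and SAP 2.2 concerns the safety and tolerability of eight weekly doses, and a long collection window is not an objective.

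**Conclusion.** The rule in SAP 11.6.2.1 is wrong as written, and it conflicts with 11.6.2.2. For an AE that starts k days after the last dose, with a stop day still missing after the query, it yields a stop before the onset and a duration of 1 − k days. For an AE that spans the last dose with a missing stop day, it can shorten the duration, for example from 17 days to 6.

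This is a minor point. It touches a derived variable that the SAP defines but does not visibly summarise. AE incidence, treatment state, seriousness counts and the primary LAR analysis do not change. The documents do not support a claim that the trial's safety conclusions are compromised.

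The result assumes a known AE start date, a recorded stop month no earlier than the onset month, and that 11.6.2.1 is the rule actually programmed. The dates used are illustrative; the formula 1 − k does not depend on them.

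**What to change.** Delete the treatment-stop cap from SAP 11.6.2.1 and state one stop-day rule, used identically in 11.6.2.1 and 11.6.2.2. After an unsuccessful data-management query, impute the last day of the recorded month, no later than the subject's last study contact or final follow-up visit (whichever is later), and never before the AE start date. Keep the December convention only for a missing month, under the same two limits.

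Dropping the cap alone would remove the negative values when the start date is known. The upper limit is added so that an imputed stop does not run past the time the subject was observed, and the floor at onset guards against any remaining impossible value.

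The cost is a sentence or two in two adjacent SAP sections and a small change to the AE derivation code. No data collection, visit or clinical procedure changes.
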